9. STATISTICAL CONSIDERATIONS

9.1 General Design Issues

Design: This is a single-blinded randomized controlled trial in which subjects will be randomized in a 1:1 fashion to receive either an expanded or standard visit with a healthcare provider about their GERD symptoms and then treated with amitriptyline or omeprazole for 8 weeks to determine whether an expanded visit can augment the effects of a medication compared to a standard visit.

Primary hypotheses:

1. Subjects who receive an expanded visit will have a greater improvement in their GERD symptoms after 8 weeks of treatment with amitriptyline or omeprazole compared to subjects who receive a standard visit.

Secondary hypothesis:

1. Patient-provider dyads in expanded visits will have a greater percentage of the total visit time spent in physiologic concordance (measured by either GSR or HRV) compared patient-provider dyads in standard visits.
2. Percentage of visit time with physiologic concordance (in GSR or HRV) will be correlated with GERD symptom improvement.
3. Subjects who experience physiologic changes similar to those elicited by mind-body techniques (i.e., decreased GSR and increased high frequency HRV) over the course of their visit (first several minutes compared to the last several minutes of the visit) will demonstrate greater improvements in GERD symptom severity than subjects who do not.

4. Healthcare providers in expanded visits will demonstrate more patient-centered non-verbal behaviors (e.g., smiles and gazes) and global impression (e.g., engaged, friendly, relaxed) compared to providers in standard visits as rated by blinded reviews of thin slices of video excerpts.
5. Patient and provider smiling at the end of study visits will be significantly associated with GERD symptom improvement 8 weeks later.

Primary outcome:

1. Change in the average daily GERD symptom severity score from baseline to the last week of the study in the expanded vs. standard group. GERD symptom severity is based on the sum of scores assessing the severity of daytime heartburn, nighttime heartburn, and acid reflux each on a 0-4 point scale (none, mild, moderate, severe, very severe; higher scores signify worse symptoms).

Secondary outcomes:

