1. Ratio of the sum of positive correlations over the sum of negative correlations in GSR (or HRV) across patient-provider encounters for standard vs. expanded visit types and for responders vs. non-responders (those with a 50% or greater improvement in their GERD symptom severity).
2. Absolute change in GSR (or high frequency HRV signal) in patient recordings from the beginning of the study visit to the end of the study visit and correlation with subsequent change in GERD symptom severity.
3. Differences in blinded ratings of 2 minute thin slices of study visit videos from the beginning to the end of the study in supportive global impressions (e.g., engagement, relaxed, patient seems pleased/satisfied) and non-verbal behaviors (e.g., smiling) between standard and expanded visit types and correlation with subsequent change in GERD symptom severity.

Validity and reliability of outcome measures:

1. Assessment of physiologic concordance has been described by a number of groups and we will be using similar methodology^{45,82}.
2. GERD symptom severity will be assessed by a daily symptom diary used by a number of other groups in medication trials and in our previous study^{64,83,84}. The average daily GERD symptom severity is based on the daily sum of scores from the first three questions assessing severity of daytime heartburn, nighttime heartburn, and acid reflux averaged over a 7 day period. The change in GERD symptom severity is calculated by subtracting the average daily GERD symptom severity score during the last 7 days of the study from the average daily GERD symptom severity score at study enrollment. The other GERD symptom questionnaires we are using have also been validated^{26,73,74}.
3. Social psychologists have developed and validated a variety of coding schemes to analyze providers' verbal and non-verbal behaviors and to link these behaviors with patient satisfaction, understanding, trust, rapport, empathy, and a variety of related factors^{9,58-63}. We will use a subset of these validated coding

schemes. Thin slices have shown high reliability and validity for behaviors such as gaze, nods, and smiles⁸⁵.

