9.2 Sample Size and Randomization

The combined standard deviation (root mean square error) in my pilot fellowship study was 1.5⁶⁴. We are conservatively assuming that this number will likely be larger in this study given the greater number of providers involved. Given 30 subjects in each group (n=60 total), 80% power, a two-sided significance test with alpha = 0.05, the minimal detectable difference (MDD) in GERD symptom severity scores between the standard and expanded groups given the estimated standard deviations (SD) is shown in the adjacent table. These MDD values are similar to those found in my fellowship study⁶⁴ and are clinically meaningful^{86,87}.

Minimal Detectable Difference Between Groups	
SD	MDD
1.5	1.10
2.0	1.47
2.5	1.84

Treatment Assignment Procedures

A randomization scheme will be devised before the start of the study by the study biostatistician who will retain the code and will be responsible for breaking the blind at the end of the study. We do not anticipate a need to break the blind during the study because we are not expecting serious adverse events to occur more frequently in one visit group than another. Randomization will be stratified by provider, with permuted block sizes of 2 and 4 with a goal to have 5-6 providers each see 10-12 subjects. If a provider cannot commit to this many visits, the study biostatistician may need to adjust the randomization scheme and we will consent additional providers.

The study biostatistician will enter the randomization scheme into REDCap and subjects will be randomized immediately prior to the study visit intervention.

If a subject drops out or is unable to complete the study, the statistician may need to rebalance the randomization scheme.

Subjects will be informed of their visit group assignment during the debriefing at the end of the second study visit.

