9.5 Outcomes

A combination of description statistics, pearson correlations, and general linear models (GLM) such as ANCOVA, will be used for analyzing the data.

Assessment	Time Points Collected	Analysis Plan	Section
Demographics, health behaviors, height & weight	Visit 1	Descriptive statistics	9.6
Daily GERD Symptom Diary	Visit 1 & Visit 2	Primary Outcome – ANCOVA analysis adjusting for baseline GERD symptom severity and visit type using follow-up GERD symptoms as the outcome.	9.5.1
GERD-HRQL	Visit 1 & Visit 2	Descriptive statistics and secondary measures of GERD symptom severity in ANCOVA analyses.	9.6
NIH PROMIS GERD			
GSRS			
Current Stress	Visit 1 (both before & after provider visit) & Visit 2	Descriptive statistics and covariate in GLM analyses.	9.6
PSS-10	Visit 1 (before provider visit) & Visit 2	GLM to determine whether perceived stress is a modifying factor for change in GSR and HRV in the context of the visit intervention	9.6
FFI	Visit 1	GLM to determine whether personality is a modifying factor for change in GERD symptoms in the context of the visit intervention	9.6
GSR & HRV	Visit 1	Secondary Outcome – GLM assessing change in GERD symptom severity and physiologic concordance in patient-provider dyads	9.5.1
Video Recording	Visit 1	Secondary Outcomes - GLM to compare the frequency of supportive provider behaviors between the standard and expanded visit groups and responders vs. non-responders (those with a 50% or greater improvement in GERD symptoms).	9.5.2
Impressions of the Study Physician	Visit 1, post-intervention	GLM to determine whether empathy and the patient-provider connection modify change in GERD symptoms in the context of the visit intervention	9.6
CARE			
HEAL Patient-Provider Connection			

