9.5.2 Secondary Outcomes

1. To analyze physiologic synchrony in GSR, first, an average slope of the GSR will be calculated in the patient and provider recordings in moving 5 second windows, offset by 1 second. Next, Pearson correlations with lag zero will be calculated over successive 15 second windows between time-locked patient and provider GSR slope values. Then, a single session index will be calculated from the ratio of the sum of the positive correlations across the entire visit divided by the sum of the absolute value of the negative correlations across the entire visit. To reduce skew, the natural logarithm of the index will be calculated. Thus, an index value of zero reflects equal positive and negative correlations, a value greater than zero reflects more concordance in GSR than not, while a value less than zero reflects less concordance in the dyad (less than 50%)⁸². These index values will be used in GLM analyses with GERD symptom severity and/or correlated with visit type.

We will also perform similar analyses on the HRV data – comparing variation in the beat-to-beat intervals over short segments of time and calculating Pearson correlation coefficients for time-locked patient and provider data for these intervals.

2. We will calculate absolute changes in both GSR and also high frequency HRV within study subjects from the beginning to the end of the study visit. We will assess the Pearson correlation between these changes and reported changes in GERD symptom severity. We will also look at absolute levels of GSR and HRV at the end of the study visit and compare those values with changes in GERD symptom severity in GLM models. As an exploratory analysis, I will test whether changes in GSR and HRV are a function of baseline perceived stress and if that relationship differs between the standard and expanded visit interventions.
3. To analyze study visit videos, 2 minute thin slices of each video at three time points (beginning, middle, and end of study visits) will be analyzed by trained and blinded coders, for the presence of 1) micro-level non-verbal supportive behaviors (e.g., gazes, smiles, nods, gestures – measured as absolute number or

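### Secondary outcome 1 and the video row of the Section 9.5 table test markers against a 50% responder split alongside planned continuous analyses, with no rule for which is the test

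*Combined protocol and SAP*

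**What the plan says.** Secondary outcome 1, given identically in Section 3 and Section 9.1, takes the GSR or HRV concordance ratio "for standard vs. expanded visit types and for responders vs. non-responders (those with a 50% or greater improvement in their GERD symptom severity". The second of these comparisons is the only link to symptoms that it names. Outcomes 2 and 3 in the same lists are instead correlated with the later change in symptom severity.

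The Section 9.5 table brings the split back for the video data, where supportive provider behaviors are compared between visit types and between "responders vs. non-responders (those with a 50% or greater improvement in GERD symptoms".

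The hypotheses and methods treat the same links on a continuous scale:

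- Secondary hypothesis 2 (Section 9.1): "Percentage of visit time with physiologic concordance (in GSR or HRV) will be correlated with GERD symptom improvement".
- Secondary hypothesis 5 (Section 9.1): "Patient and provider smiling at the end of study visits will be significantly associated with GERD symptom improvement 8 weeks later".
- GSR and HRV row of the Section 9.5 table: "GLM assessing change in GERD symptom severity and physiologic concordance in patient-provider dyads".
- Section 9.5.2, item 1: "These index values will be used in GLM analyses with GERD symptom severity and/or correlated with visit type".
- Section 9.5.2, item 3: a Pearson correlation of each video variable with improvement, and a GLM with smiling as a predictor.

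No section gives a reason for the 50% cut, an expected responder rate, an order of precedence between the two forms, or an adjustment for running both.

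**The concern.** The symptom score is a 7-day average of a daily sum running from 0 to 12 (three items scored 0 to 4). A 50% cut treats 0% and 49% improvement as the same result. Because it is a percentage, it also sets a different bar for different patients: at the entry minimum of 3 points a responder must improve by 0.5 × 3 = 1.5 points, while a patient entering at 9 must improve by 0.5 × 9 = 4.5. The plan's detectable differences and its primary ANCOVA both work in absolute points, so the responder rule departs from the trial's own scale.

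These links carry the mechanism aims. If the responder contrast is read as the test, as the definition of secondary outcome 1 suggests for concordance, a real association is more likely to be missed. If both forms are run and neither ranks first, the more favorable can be reported.

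**Working it through.** **The plan's own power figure.** Section 9.2 gives the only one: "Given 30 subjects in each group (n=60 total), 80% power, a two-sided significance test with alpha = 0.05", with detectable differences of 1.10, 1.47 and 1.84 at SDs of 1.5, 2.0 and 2.5. A two-sample t-test with 58 degrees of freedom (noncentral t) returns 1.103, 1.471 and 1.839, so the table reproduces. It covers the comparison of visit types; no power is stated for any marker or responder analysis.

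**Inputs.** From the plan: n = 60, two-sided alpha 0.05, cut at 50% improvement. Assumed, because the plan does not give them: responder share p from 20% to 50%, a true marker-symptom correlation of 0.35, and normal marker and outcome. The only related figure in the documents is the placebo response of up to 40% in the background (Section 2.1).

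**Information kept by the split.** For a normal outcome cut so that a share p respond, the efficiency relative to the continuous score is E = φ(z)² / [p(1 − p)], where z is the normal quantile at the cut and φ the normal density. The correlation shrinks by √E.

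- p = 0.50: φ(0) = 0.3989; E = 0.1592 / 0.25 = 0.637; loss 36.3%.
- p = 0.25: φ(0.6745) = 0.3178; E = 0.1010 / 0.1875 = 0.539; loss 46.1%.

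**Power.** By Fisher's z, power = Φ(atanh(r)·√57 − 1.96). For the continuous score with r = 0.35: atanh(0.35)·√57 = 2.759, so power = Φ(0.799) = 79%. For the split, r is replaced by 0.35·√E. Simulated trials of 60 give 79% to 80% for the continuous test and the last column below for the split.

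| Responder share | Information lost | Equivalent n of 60 | Power of split, Fisher z | Power of split, simulated |
|---|---|---|---|---|
| 50% | 36.3% | 38.2 | 58% | 59% |
| 40% | 37.8% | 37.3 | 57% | 58% |
| 30% | 42.4% | 34.5 | 54% | 55% |
| 25% | 46.1% | 32.3 | 51% | 52% |
| 20% | 51.0% | 29.4 | 47% | 47% |

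**Effect of the percent-change rule.** The formula cuts the same variable that the continuous test uses, whereas the plan cuts percent change. An illustrative simulation of the actual rule (assumed baseline of 3 plus a gamma variable with mean 2, SD of change 1.5 to 2.5) gives a loss of about 41% to 53% relative to absolute change, for responder shares of roughly 27% to 51%. The 36% to 46% is therefore not inflated by the simplification.

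**Two tests of one link.** With no true association and each test at 5%, the simulated chance that at least one is significant is 7.7% to 8.6% per marker over responder shares of 50% to 20%. Two independent tests would give 1 − 0.95² = 9.75%; the figure is lower because the two tests are strongly correlated.

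**The case against.** A reader might infer that the trial discards more than a third of its symptom information. The documents do not support that. Continuous analyses are planned for both kinds of marker that are also split: the concordance index in the Section 9.5 table and Section 9.5.2, and the video variables in secondary outcome 3 and Section 9.5.2. The detailed methods in Section 9.5.2 contain no responder test. The roughly 79% power of the continuous analysis remains available, and the loss belongs to the responder comparison alone.

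Nor are all markers affected. Secondary outcome 2, within-patient change in GSR or HRV, has no responder split. Only hypothesis 2 is literally worded as a correlation; hypothesis 5 speaks of association, and hypothesis 3 compares patients grouped by their physiologic change. The primary ANCOVA uses the continuous score.

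It is also fair to say that the percentages depend on a responder share and a normal outcome that the plan does not supply, that a correlation of 0.35 lies close to what 60 patients can detect with 80% power (0.355), and that an error rate near 8% on a secondary analysis is a modest excess.

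All of this stands, and it limits the point. It does not settle which analysis is the test. Secondary outcome 1 names only the responder contrast for concordance against symptoms, hypothesis 2 calls for a correlation, and the and/or in Section 9.5.2 leaves even the continuous analysis optional.

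**Conclusion.** The point holds for the concordance index in secondary outcome 1 and for supportive behaviors in the video row of the Section 9.5 table. Each is related to symptoms in two forms, and the plan does not say which counts. The responder form is clearly the weaker: it loses about 36% to 46% of the information at responder shares of 50% down to 25%, and 51% at 20%. At n = 60 and an assumed correlation of 0.35, its power is about 52% to 59% over the 25% to 50% range, against about 79% for the continuous form. Running both without adjustment raises the false-positive chance from 5% to roughly 8% per marker. The loss and power figures assume normality and a responder share absent from the plan. This should be corrected before analysis, but it does not threaten the trial's primary conclusion.

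**What to change.** In secondary outcome 1 (Sections 3 and 9.1) and the video row of the Section 9.5 table, name one continuous analysis as the test of each marker-symptom link: a GLM of week-8 GERD severity on the marker, adjusted for baseline severity, in line with the ANCOVA in Section 9.5.1. State whether visit type is also in the model, as it is in that ANCOVA.

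The baseline term is needed. The hypotheses concern improvement, and an unadjusted week-8 score would mix improvement with initial severity. With baseline in the model, using week-8 severity or change as the outcome gives the same marker effect apart from sign, so the wording of the GSR and HRV row can be aligned without altering its intent.

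In Section 9.5.2, item 1, replace the and/or with a definite statement that the index is tested against symptom severity in this model and, separately, compared between visit types. In item 3, present the Pearson correlations as descriptive beside the named model. Label the responder comparison descriptive wherever it appears.

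The cost is wording only: no new data, visits or patients. What is given up is the responder contrast as a formal test; responder results can still be tabulated.

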9.2 Sample Size and Randomization

The combined standard deviation (root mean square error) in my pilot fellowship study was 1.5⁶⁴. We are conservatively assuming that this number will likely be larger in this study given the greater number of providers involved. Given 30 subjects in each group (n=60 total), 80% power, a two-sided significance test with alpha = 0.05, the minimal detectable difference (MDD) in GERD symptom severity scores between the standard and expanded groups given the estimated standard deviations (SD) is shown in the adjacent table. These MDD values are similar to those found in my fellowship study⁶⁴ and are clinically meaningful^{86,87}.

Minimal Detectable Difference Between Groups	
SD	MDD
1.5	1.10
2.0	1.47
2.5	1.84

Treatment Assignment Procedures

A randomization scheme will be devised before the start of the study by the study biostatistician who will retain the code and will be responsible for breaking the blind at the end of the study. We do not anticipate a need to break the blind during the study because we are not expecting serious adverse events to occur more frequently in one visit group than another. Randomization will be stratified by provider, with permuted block sizes of 2 and 4 with a goal to have 5-6 providers each see 10-12 subjects. If a provider cannot commit to this many visits, the study biostatistician may need to adjust the randomization scheme and we will consent additional providers.

The study biostatistician will enter the randomization scheme into REDCap and subjects will be randomized immediately prior to the study visit intervention.

If a subject drops out or is unable to complete the study, the statistician may need to rebalance the randomization scheme.

Subjects will be informed of their visit group assignment during the debriefing at the end of the second study visit.

9.3 Definition of Populations

For analyses including the intervention group type, we will analyze our data according to which visit intervention subjects received (standard or expanded). We do not anticipate any discrepancies between what subjects were assigned to receive by randomization and what they actually received. Study visit type will be guided by a written script that the providers will follow during the visit. The actual intervention received will also be verified by reviewing study video recordings.

The intent to treat analysis will include all randomized subjects who received a study visit intervention. The per protocol analysis will include all individuals who received a study visit intervention and completed the follow-up questionnaires at 8

weeks.

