5. STUDY INTERVENTIONS

5.1 Interventions, Administration, and Duration

Subjects will be randomized to receive either a “standard visit” or an “expanded visit” with a study provider. The standard visit is based on a high quality, empathic, conventional primary care encounter. The expanded visit is based on an integrative medicine consultation. Both visits are based on a script of questions and statements to the patient/subject (see Appendix E). The standard visit script includes questions about GERD history, symptoms, prior evaluation and treatments, and past medical history as well as a brief physical exam. The expanded visit script includes the same questions as the standard visit script plus additional questions that inquire about the modalities of their GI symptoms (e.g., nature of the reflux taste, sensation of heartburn pain and/or abdominal fullness, time of day better/worse), details about non-GI symptoms, quality of sleep, the effect of the weather on symptoms, food cravings and aversions, menstrual flow, fears/phobias, and overall temperament. In this way, the expanded visit tries to understand the patient’s/subject’s constitution in a way that many systems of integrative medicine attempt to do. To reduce the potential for introducing bias by using the words “standard” and “expanded”, the visit templates that the study providers will follow will simply refer to the number of questions to be asked on the template (e.g., 6 Question Template).

At the end of both the standard and expanded visits, the provider will recommend the subject take the study medication and describe how to take it and what to expect. Subjects will receive the same scripted advice in both groups. Each subject will receive an 8-week supply of amitriptyline or omeprazole with instructions for how to take it (10 mg daily at bedtime or 20 mg daily when waking up, respectively).

In our pilot study⁶⁴ we did not limit the amount of time spent with the study subject. On average, the standard visit lasted 18 minutes (range 11-32 minutes) and the expanded visit lasted 42 minutes (range 23-74 minutes). The study providers will be instructed to maintain equal empathy in both groups (e.g., kind and friendly manner, maintain eye contact, active listening and repeating back the patient’s words, expressions of empathy). Thus, the main differences between the visits will be the length of time spent with the subject and the additional questions that are asked.

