5.2 Handling of Study Interventions

To minimize potential bias that could affect study staff interactions with subjects, the subject will be randomized immediately before the study visit and the study provider will receive the appropriate study visit script. At the time of consent, study subjects will not be informed about the two different interview types or that part of the study involves testing the effect of the doctor-patient interaction on response to treatment. Concealment of these aspects of the study protocol is essential to maintaining the validity of the study as data suggests that patients' responses change when they know that the doctor-patient interaction is being studied^{69,70}. The study PI, or another study team member, will notify subjects at their follow-up study visit, after the exit interview, that there were two possible types of physician visits, that this aspect of the study was concealed from them initially, and of the rationale for doing so. A script outlining this planned debriefing is present in Appendix F. We believe that this intervention is minimal risk and that our plan meets the federal criteria for permitting alteration of some elements of informed consent⁷².

Subjects will be informed about taking amitriptyline or omeprazole as part of the study during the consent process and the study physician will discuss this with them during the study visit. Subjects will receive a container with an 8 week supply of the medication from a study team member at the end of the study visit.

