9.5.1 Primary Outcome

1. Change in the average daily GERD symptom severity score from baseline to the last week of the study in the expanded vs. standard group. GERD symptom severity is based on the sum of scores assessing the severity of daytime heartburn, nighttime heartburn, and acid reflux each on a 0-4 point scale (none, mild, moderate, severe, very severe; higher scores signify worse symptoms). We will use ANCOVA for the primary analysis, adjusting for baseline GERD symptom severity and visit type assignment using the 8 week follow-up GERD symptom severity as the outcome. Potential moderators that will be assessed in exploratory analyses will include gender (both patient and provider), race, visit length, patient stress, personality type, and perceived connection with/empathy of the provider.

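### Section 9.3 groups subjects by visit received, Section 9.5.1 models visit type assigned, and nothing says which governs the primary analysis

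*Combined protocol and SAP*

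**What the plan says.** Section 9.3 opens with a general rule for any analysis that involves the intervention group: "we will analyze our data according to which visit intervention subjects received (standard or expanded". It then states an expectation, "We do not anticipate any discrepancies between what subjects were assigned to receive by randomization and what they actually received", and a check, "The actual intervention received will also be verified by reviewing study video recordings".

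The next paragraph of 9.3 defines two analysis sets. For the first, "The intent to treat analysis will include all randomized subjects who received a study visit intervention". The per-protocol set adds completion of the 8-week questionnaires. Both sentences say who is counted. Neither says how those subjects are grouped, and the per-protocol sentence does not require that the visit received match the visit assigned.

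Section 9.5.1 specifies the primary ANCOVA of the 8-week symptom score as "adjusting for baseline GERD symptom severity and visit type assignment". The table in 9.5 describes the same model with visit type alone, without saying assigned or received. Sections 9.5.2 and 9.6 do not say either.

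**The concern.** Two sections give different group variables for one model. The primary ANCOVA includes visit type, so the general rule in 9.3 applies to it and asks for visit received. Section 9.5.1 asks for visit assigned. Read literally, the plan also has an analysis labelled intent-to-treat that is grouped as treated.

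Randomisation protects the comparison of subjects as assigned. Whether a visit is delivered in full can depend on the patient, for example on severity or engagement. Moving such a subject to the other group on the basis of what happened in the room gives up that protection, and the resulting bias can favour either visit type. An analyst who met a mismatch could defend either grouping from the text, and might choose after outcomes are known.

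**Working it through.** **1. The texts side by side.**

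| Place | Group variable |
|---|---|
| 9.3, opening sentence | Visit received, for every analysis with visit type |
| 9.3, intent-to-treat and per-protocol sentences | None stated; inclusion only |
| 9.5 table, primary outcome row | Visit type, unspecified |
| 9.5.1 | Visit type assigned |

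No sentence reconciles the first row with the last.

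**2. Can the two differ?** A wrong script is unlikely: by 5.2, "the subject will be randomized immediately before the study visit and the study provider will receive the appropriate study visit script". Classing a visit from video is less clear. Section 5.1 says "The expanded visit script includes the same questions as the standard visit script plus additional questions", so an expanded visit that stops early looks increasingly like a standard one. Pilot visit lengths in 5.1 ran 11 to 32 minutes (standard) and 23 to 74 minutes (expanded); the overlap is max(11, 23) = 23 to min(32, 74) = 32 minutes. The text available gives no rule for classing such a visit. The Appendix E scripts were not in that text. The randomised type is always known.

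**3. The plan's own figures.** Inputs from 9.2: 30 per arm, 80% power, two-sided alpha 0.05, SD 1.5, 2.0 or 2.5. For a two-sample t test with 58 degrees of freedom, the noncentrality is d / (SD × √(2/30)). Solving for 80% power gives d = 1.103, 1.471 and 1.839, which matches the stated 1.10, 1.47 and 1.84.

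**4. Effect of relabelling one subject.** Take 30 per arm, no true effect and equal arm means, and let r be the subject's deviation from the arm mean on the baseline-adjusted outcome. Removing the subject moves one mean by r/29 and adding the subject moves the other by r/31, so

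shift = r × (1/29 + 1/31) = 0.0667 × r.

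| SD | Shift at r = 1 SD | Minimal detectable difference | Ratio |
|---|---|---|---|
| 1.5 | 0.100 | 1.103 | 9.1% |
| 2.0 | 0.133 | 1.471 | 9.1% |
| 2.5 | 0.167 | 1.839 | 9.1% |

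The sign follows the sign of r. With no relabelling the shift is 0.

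**5. Several mismatches in one direction (assumed range).** Suppose k of the 30 subjects assigned to expanded visits are classed as standard, there is no true effect, and these subjects would score g = 1.5 points worse than the other expanded-assigned subjects whatever visit they had. As-received grouping then gives a spurious difference of 2kg/(30 + k):

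- k = 1: 3.0/31 = 0.10, type I error about 5.7%
- k = 2: 6.0/32 = 0.19, about 7.6%
- k = 3: 9.0/33 = 0.27, about 10.6%

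The type I errors hold SD at 1.5. Grouping as randomised stays unbiased in this setting. Both k and g are assumptions.

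**6. Price of grouping as randomised.** If one of 30 in one arm gets the other visit and the true difference is 1.103 at SD 1.5, the as-randomised difference is 1.103 × 29/30 = 1.067, and power falls from 80.0% to 77.3%.

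**The case against.** The strongest reply is that the primary analysis is already settled. Section 9.5.1 is the specific provision and uses the assigned type, 9.3 itself contrasts assigned with received, and a statistician who lets the specific override the general would group as randomised. That reading is reasonable. The text does not state it, though, and the opening rule in 9.3 is explicit and general.

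The trigger is also remote. There is one scripted visit, the script is issued just beforehand, the principal investigator reviews recordings for fidelity, and no mismatch is expected. This stands, and it is why the point is minor.

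The visit-length argument is only supporting. Section 5.1 defines visit types by script, not by duration. A visit cut short is a hypothetical, a completeness criterion might be in Appendix E, and verifying on video may mean a fidelity check rather than relabelling. These points limit how much weight the overlap can bear. They do not remove the conflict between 9.3 and 9.5.1.

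Finally, writing a classing rule before the blind is broken is a modest safeguard, since Section 3 says providers and the research team know the visit type. That also stands: the earlier the rule is written, the better.

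**Conclusion.** The point holds as a minor inconsistency. Section 9.3 states a grouping rule that departs from the randomised comparison whenever received and assigned types differ, 9.5.1 states another, and the documents do not rank them.

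The expected numerical effect is nil if 9.3's expectation is met. Otherwise the size is unknown, because no mismatch rate is given. The 9% figure is a unit effect for one relabelled subject and not a forecast. It assumes 30 per arm, no true effect and a subject one SD from the arm mean. The power figures use a plain two-sample t test; baseline adjustment could be more efficient, but the documents give no correlation between baseline and follow-up.

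Confidence is high that the wording conflicts. Whether bias would arise depends on a mismatch occurring.

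**What to change.** Replace the opening sentence of 9.3 with:

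> The primary and other intent-to-treat comparisons of visit type group subjects by the visit type to which they were randomised, as in 9.5.1; analysis by visit received is a sensitivity analysis. Per-protocol, dyad physiology and provider behaviour analyses may group by visit received if labelled as such, using a rule for classing visits from video that is written before the blind is broken.

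Leave the rest of 9.3 as it is. Its intent-to-treat sentence still sets who is included: randomised subjects who had a visit of either type. The wording takes the primary analysis to be intent-to-treat, which 9.3 does not say, so the study team should confirm that.

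The cost is one sentence, plus a short classing rule if as-received analyses are kept. No new data are needed, and sample size and the table in 9.2 do not change. Without a mismatch there is no downside. With one, there is one extra sensitivity analysis and a loss of about 3 percentage points of power per one-way mismatch (80.0% − 77.3% = 2.7).
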